1. ≥ 18 years of age
2. First single focal unilateral left hemisphere lesion with diagnosis verified by brain imaging (MRI or CT scans) that occurred at least 6 months prior
3. Pre-morbidly right handed
4. Pre-morbidly fluent English speaker
5. Cognitive function sufficient to understand the experiments and follow instructions (per interview with Speech Pathologist)
6. A baseline Aphasia Quotient score between 10 to 94 out of 100 points on the Western Aphasia Battery (neither completely without language comprehension/expression nor fully recovered from aphasia).

Exclusion Criteria:

1. Ongoing use of CNS-active medications
2. Ongoing use of psychoactive medications, such as stimulants, antidepressants, and anti-psychotic medications
3. Presence of additional potential tDCS risk factors:
 - Damaged skin at the site of stimulation (i.e., skin with ingrown hairs, acne, razor nicks, wounds that have not healed, recent scar tissue, broken skin, etc.)

- Presence of an electrically, magnetically or mechanically activated implant (including cardiac pacemaker), an intracerebral vascular clip, or any other electrically sensitive support system
 - Metal in any part of the body, including metal injury to the eye (jewelry must be removed during stimulation)
 - A history of medication-resistant epilepsy in the family
 - Past history of seizures or unexplained spells of loss of consciousness during the previous 36 months
4. Pregnancy in women, as determined by self-report

Visit Schedule

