In this pilot study, 24 participants will be accepted from our referral sources in the department of Neurology and Physical Medicine. There will be 2 measurement periods before the training starts, separated by 3-14 days in order to establish baseline word-finding performance on selected trained and untrained word lists. Following the lead-in period, subjects will participate in a cross-over design training period to compare the two tDCS conditions (1mA anodal vs. sham). The training portion of the study will occur over a total of 3 weeks. During that time, subjects will attend five consecutive, 60-minute training sessions under treatment condition one (anodal vs. sham tDCS), followed by a 1 week rest interval, and then another five consecutive sessions of training under treatment condition two. Order of training word lists and tDCS stimulation condition will be counterbalance across participants. Subjects will undergo four additional evaluations throughout the course of the study, two of which will occur immediately after each of the training conditions (discharge), and the other two of which will occur 1 week after each training condition (follow-up). All study procedures will be administered or supervised by the research coordinator or another licensed Speech-Language Pathologist. All visits will be conducted in the clinical robotics and non-invasive brain stimulation suite at the Feinstein.

Lead-in Period

- Week 1, Visit 1 (approximately 60 minutes)
 - Baseline outcome measures
 - Medical screening
 - Consent
- Week 2, Visit 2 (approximately 60 minutes each)
 - Baseline outcome measures

Training Period Phase I

- Week 3, Visit 3-6 (approximately 60 minutes)
 - 20 min of stimulation condition 1 (sham or anodal tDCS) and 20 min of computerized word-picture matching therapy
- Week 3, Visit 7 (approximately 90 minutes)
 - 20 min of stimulation condition 1 (sham or anodal tDCS) and 20 min of computerized word-picture matching therapy
 - Condition 1 discharge outcome measures

Follow Up Testing Phase I

- Week 4, Visit 8 (approximately 60 minutes)
 - Condition 1 follow-up outcome measures

Training Period Phase II

- Week 5, Visit 9-12 (approximately 60 minutes)
 - 20 min of stimulation condition 2 (sham or anodal tDCS) and 20 min of computerized word-picture matching therapy
- Week 5, Visit 13 (approximately 90 minutes)
 - 20 min of stimulation condition 2 (sham or anodal tDCS) and 20 min of computerized word-picture matching therapy

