 - Condition 2 discharge outcome measures

Follow Up Testing Phase II

- Week 6, Visit 14 (approximately 60 minutes)
 - Condition 2 follow-up outcome measures

Schedule Chart

	Screen 1	Screen 2	Tx Condition 1		Cond 1 FU	Tx Condition 2		Cond 2 FU
	Visit 1	Visit 2	Visit 3-6	Visit 7	Visit 8	Visit 9-12	Visit 13	Visit 14
Informed Consent	X							
Medical Hx	X							
Medical FU		X						
Demographic Info	X							
Inclusion Criteria	X							
Neurological Exam	X							
Medication check	X							
Outcome Measures	X	X		X	X		X	X
tDCS and Aphasia tx			X	X		X	X	

Clinical Outcome Measures

Naming Probes (Primary Measure):

Picture naming accuracy will be assessed across two word lists, which were developed in a previous study (4). Each word list is comprised of a total of 75 trained and untrained nouns, which are controlled for word-frequency, semantic content, and word length, and depicted with color pictures presented on a laptop. Subjects will be provided with a different word list for each condition (sham vs. anodal tDCS), and asked to name each picture as soon as they see it. Responses will be audio/visually recorded for later transcription and scoring by an SLP. The first complete response will be used to determine the accuracy score. The outcome measure will be change in naming accuracy of trained items (task learning) and untrained items (learning generalization) in each condition.

Aphasia Battery (Secondary Measures):

A set of brief subtests from larger aphasia batteries will be used to assess changes in verbal expression and fluency in subjects with chronic expressive aphasia. Audio/Video recordings will be made of speech-language assessments for review and scoring by approved clinicians.

-“Diadochokinetic Rate” and “Increasing Word Length,” subtests of the Apraxia Battery for Adults (ABA-2): The ABA-2 is a valid and reliable measure of changes in motor speech across isolated speech sounds, multisyllabic utterances, and connected speech samples. Together, these subtests take approximately 5 minutes to administer and derive an apraxia impairment profile score (42, 45, 46).

-Generative Naming: Generative Naming is a commonly used clinical measure of verbal fluency and semantic memory in individuals with aphasia. It has been used frequently in the tDCS literature as a sensitive metric of changes in verbal fluency (38, 39, 43).

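### No re-check for a newly started excluded drug, seizure or blackout is scheduled before the second stimulation block, and no rule says when to withhold a session (minor, safety)

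*Combined protocol and SAP*

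**What the plan says.** The Exclusion Criteria bar ongoing use of CNS-active drugs and, as a separate item, "Ongoing use of psychoactive medications, such as stimulants, antidepressants, and anti-psychotic medications". Among the tDCS risk factors they list "Past history of seizures or unexplained spells of loss of consciousness during the previous 36 months".

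In the Schedule Chart the row "Medication check" is marked at Visit 1 only, as are the rows for medical history, inclusion criteria and neurological examination. A row labelled Medical FU is marked at Visit 2 only, under the second screening column. The document does not say what it covers, and the narrative Visit Schedule lists only baseline outcome measures for that visit. From Visit 3 onward the only rows marked are outcome measures and tDCS with aphasia treatment. Visit 8, the one visit between the two blocks, lists only follow-up outcome measures.

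The safety text covers other things. Protection Against Risk provides for observation during stimulation, a cold compress for redness, and stopping if the participant asks. Recruitment and Informed Consent allows withdrawal at any time. Data and Safety Monitoring provides for an aggregate review by the principal investigator every 4 months.

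**The concern.** The exclusions describe states and events that can start during a six-week course. The trial thought them important enough to keep people out at entry, yet ten stimulation sessions follow (five plus five) with no scheduled question about them. A participant who had a blackout, or was prescribed an antidepressant, after Visit 2 could start the second block without anyone having been told to ask. If staff did learn of it, the protocol would not tell them what to do.

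Relying on participants to volunteer such an event is less secure here than in most trials, because entry allows "A baseline Aphasia Quotient score between 10 to 94 out of 100 points on the Western Aphasia Battery". The protocol sees the difficulty at consent, where the legally authorised representative or next of kin is routinely included, but it gives that person no role at later visits.

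What is at stake is participant safety judged by the trial's own criteria, not the analysis.

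**Working it through.** The plan gives no figure to reproduce. The check has two parts: which scheduled items could detect a new event, and how old the last one is when the second block starts.

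**Items that could detect a new event**

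- Visit 1: medical history, inclusion criteria, neurological examination, medication check.
- Visit 2: Medical FU, content undefined.
- Visits 3-7 (block 1): none.
- Visit 8 (between blocks): none.
- Visits 9-13 (block 2): none.

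The other safety provisions do not fill the gap. Observation and the cold compress act during or after stimulation. The written means of stopping or withdrawing start with the participant. The 4-monthly review is in aggregate, and one participant's course lasts about six weeks.

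**Age of the last check**

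Inputs from the Visit Schedule: Visit 1 in week 1, Visit 2 in week 2, block 1 in week 3, Visit 8 in week 4 (one week after block 1), block 2 in week 5, and five consecutive sessions per block. On the baseline visits it says: "There will be 2 measurement periods before the training starts, separated by 3-14 days".

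Assumptions: visits fall on weekdays of their labelled weeks, and each block starts on a Monday. Let day 0 be the Monday of week 1. Then:

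- Visit 1 = days 0 to 4; Visit 2 = days 7 to 11. The gap is 7 − 4 = 3 to 11 − 0 = 11 days, inside the permitted 3-14.
- Visit 3 = day 14; Visit 7 = day 18; Visit 8 = 18 + 7 = day 25; Visit 9 = day 28; Visit 13 = day 32.

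Results:

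- Medication check to Visit 9: 28 − 4 = 24 to 28 − 0 = 28 days.
- Medical FU to Visit 9: 28 − 11 = 17 to 28 − 7 = 21 days.
- Medical FU to Visit 3: 14 − 11 = 3 to 14 − 7 = 7 days.
- Visit 8 to Visit 9: 28 − 25 = 3 days, with no medical item at Visit 8.
- With a check added at Visit 9, the oldest check at any block 2 session: 32 − 28 = 4 days.

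**Who is exposed in block 2**

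Order is counterbalanced (Visit Schedule; Randomization), so about half of participants have the anodal condition second. In the sham condition the current ramps up briefly and is not sustained (tDCS Application).

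**The case against.** The strongest reply is that the risk is small and largely covered in practice. The protocol calls tDCS a non-significant risk, and the stimulation is 1 mA for 20 minutes. About half of participants get only sham in block 2. Participants must be able to understand the experiments and follow instructions, as judged at interview with a speech pathologist. A coordinator or licensed speech-language pathologist runs or supervises every visit and may well ask. All of this stands, and it is why the point is minor. It does not remove the omission: nothing requires or records the question, and no action follows from the answer.

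A reader might infer more than the documents support:

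- *That both blocks are equally affected.* Medical FU sits under the second screening visit and plausibly updates medical status 3-7 days before block 1. The gap matters chiefly before block 2.
- *That the gap reaches 35 days.* That takes the full 14 days between Visits 1 and 2, then 7, then 14 (14 + 7 + 14 = 35). It would put Visit 1 before its labelled week.
- *That pregnancy and skin carry the same weight.* The criterion "Pregnancy in women, as determined by self-report" is a separate exclusion, not one of the listed tDCS risk factors. The criterion "Damaged skin at the site of stimulation" is one of them, but staff would see the skin when placing electrodes.
- *That the protocol permits stimulating someone newly ineligible.* It does not say so. The gap is that nothing scheduled would find that person.
- *That a drug started between blocks biases the anodal-sham comparison.* The documents give no rate of such starts and no basis for a direction, so no effect on the analysis can be claimed.

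**Conclusion.** The concern holds as a minor safety point. After the undefined medical follow-up at Visit 2, nothing scheduled would detect a newly started excluded drug, or a new seizure or unexplained loss of consciousness, before or during block 2. No rule tells staff when to withhold stimulation.

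At Visit 9 the only medication check is 24-28 days old and the medical follow-up 17-21 days old. Both ranges rest on the week labels and Monday block starts; the document itself does not fix these dates. The intervals measure how stale the checks are, not how likely an event is. The documents give no event rate, so none is offered.

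**What to change.** In the Schedule Chart, mark the medication check at Visit 9. At the same visit ask about any seizure or loss of consciousness since the last check, putting the question to the participant and, where needed, to the representative or next of kin. Do this for every participant whatever the condition, because staff are blinded to it.

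Add one sentence: if any item is newly positive, stimulation is withheld pending the investigator's decision. The clinical content of that decision can be left to the investigators.

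Optionally, repeat the check at Visit 3 so that both blocks are handled alike, and add pregnancy to the same form.

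The cost is one mark in the chart (two with Visit 3), one sentence, a short form and a few minutes of time from staff already present. The downside is an occasional deferred session, which breaks the run of five consecutive sessions for that participant. An event within block 2, up to 4 days after the check, would still not be asked about formally.

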This self-administered computerized anomia treatment was reported on in a previous study, and demonstrated to be helpful in improving naming accuracy of individuals with aphasia (4). Subjects are asked to perform a 20-minute picture-word matching task following receipt of either sham or anodal tDCS.

Randomization

A single-subject cross-over design will be used to compare two tDCS conditions (1mA anodal vs. sham). The order of anodal or sham stimulation will be counterbalanced across participants, and determined using a random number generator.

Blinding

This is a double blind study. The tDCS device will be covered such that the administrator will code each stimulation condition as either switch “up” or switch “down,” but will remain blinded to which code is anodal vs. sham stimulation. In this way, all investigators interacting with patients will remain unaware of stimulation condition. For the sham condition, the stimulation automatically ramps down after 30 seconds because the perceived sensation of tDCS on the skin has been reported to fade after this period (21). Consequently, participants will also stay blinded to stimulation condition.

Statistical Considerations and Data Analysis

SPECIFIC AIM 1: To evaluate whether anodal tDCS preceding aphasia therapy significantly improves picture naming in individuals with post-stroke aphasia.

Methods to address specific aim 1: A Wilcoxon signed-rank test will be used to compare naming accuracy scores pre and post anodal tDCS condition across participants.

SPECIFIC AIM 2: To compare naming performance between intervention conditions (tDCS and sham stimulation).

Methods to address specific aim 2: If neuromodulation preceding treatment is effective for promoting recovery in language impairment, as it is in robotic hemiplegia treatment, we expect the improvement in naming accuracy to be greater following anodal tDCS compared with sham tDCS. This will be examined with a 2x2 repeated measures ANOVA for both treated and untreated items with stimulation type (A-tDCS,S-tDCS) and time (T1, T2) as factors.

SPECIFIC AIM 3: To compare naming performance between severity groups (high vs. low functioning aphasia as determined by admission Western Aphasia Battery scores (WAB)).

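### The plan does not provide for masking the naming scorer to visit, which leaves Aim 1's pre-post test open to leniency toward post-training recordings

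*Combined protocol and SAP*

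**What the plan says.** All places are in the combined protocol and SAP.

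- **Scoring (Clinical Outcome Measures, Naming Probes).** "Responses will be audio/visually recorded for later transcription and scoring by an SLP." The scoring rule is "The first complete response will be used to determine the accuracy score." The endpoint is a change score: "The outcome measure will be change in naming accuracy of trained items (task learning) and untrained items (learning generalization) in each condition."
- **Blinding.** The section opens "This is a double blind study." The device switch is coded up or down, and the administrator does not know which position is anodal. It continues "In this way, all investigators interacting with patients will remain unaware of stimulation condition" and, for patients, "Consequently, participants will also stay blinded to stimulation condition." Every statement is about stimulation condition. Neither visit nor an offline scorer is mentioned.
- **Staffing (Visit Schedule).** "All study procedures will be administered or supervised by the research coordinator or another licensed Speech-Language Pathologist." The plan does not say whether the scoring SLP is one of these people.
- **Aim 1 analysis (Statistical Considerations).** "A Wilcoxon signed-rank test will be used to compare naming accuracy scores pre and post anodal tDCS condition across participants." The test has no sham term.
- **Aim 2 analysis (same section).** A two-by-two repeated measures ANOVA, stimulation type by time, for treated and for untreated items.

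Independent scoring is mentioned only for the connected speech sample, a secondary measure, and not in relation to visit.

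**The concern.** Two different facts could influence a scorer: which stimulation the participant received, and whether the recording was made before or after training. The plan addresses the first for participants and for staff in contact with them. It says nothing about the second.

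For Aim 1 the second is the one that counts. The test compares post with pre scores in the anodal condition alone, so every recording in it carries the same condition and blinding to condition cannot balance anything. If borderline responses are accepted more readily on recordings known to be post-training, the extra items go straight into the estimated improvement.

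Some judgement is unavoidable. Participants may have an Aphasia Quotient as low as 10, and someone must decide which response is the first complete one and whether it is correct. The plan gives no acceptance criteria, second scorer or agreement check. At stake is whether a significant Aim 1 result on the primary measure reflects better naming or more generous scoring.

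**Working it through.** The plan gives no alpha, SD of change, effect size or power calculation, so there is no stated figure to reproduce. The check has two parts.

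**1. Which comparisons does a visit-related shift reach?**

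Let Δ_A and Δ_S be the true changes under anodal and sham, and b the average extra credit given to post-training recordings.

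- Aim 1 observes Δ_A + b. The shift stays in full.
- Aim 2's stimulation-by-time contrast observes (Δ_A + b) − (Δ_S + b) = Δ_A − Δ_S. The shift cancels if it is the same in both conditions, as expected when the scorer does not know the condition.

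**2. How large could the effect on Aim 1 be?**

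Inputs:
- n = 24 (Visit Schedule) and n = 12 (Protection of Human Subjects). The two sections differ, which is a separate matter, so both are shown.
- Test: Wilcoxon signed-rank (Statistical Considerations, Aim 1).
- Assumed, not in the documents: two-sided alpha 0.05; normally distributed change scores with SD 1; no true change; constant shift b of 0, 0.1, 0.25 or 0.5 SD.

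Method: 4,000 simulated trials per setting. Aim 1 is tested on x ~ N(b, 1). For the comparison of conditions, a signed-rank test is applied to the paired difference of two independent N(b, 1) change scores. The Monte Carlo standard error is at most √(0.5 × 0.5 / 4000) ≈ 0.008.

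| Shift b (SD of change) | Aim 1, n=24 | Aim 1, n=12 | Anodal minus sham, n=24 | Anodal minus sham, n=12 |
|---|---|---|---|---|
| 0 | 0.050 | 0.044 | 0.048 | 0.040 |
| 0.1 | 0.072 | 0.051 | 0.047 | 0.042 |
| 0.25 | 0.208 | 0.115 | 0.052 | 0.040 |
| 0.5 | 0.632 | 0.322 | 0.049 | 0.040 |

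A rough check by normal approximation: the standardised shift is b√n, and the rejection rate is about Φ(b√n − 1.96) + Φ(−b√n − 1.96).

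- n=24, b=0.5: b√n = 2.449, rate about 0.69.
- n=12, b=0.5: b√n = 1.732, rate about 0.41.

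The simulated rates are somewhat lower, as expected for a rank test in small samples, and they follow the same pattern. The Aim 1 rate climbs with the shift and with n. The comparison between conditions stays at 0.04 to 0.05 throughout.

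**The case against.** **The plan is silent; it does not say the scorer is unmasked.** This stands. A reader might infer that the scorer knows the visit, or that the SLPs who run sessions also score them. Neither is stated. The supported claim is that the plan makes no provision for masking to visit.

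**Aim 2 is not threatened in the same way.** This largely stands. A reader might infer that the sham-controlled comparison is compromised too. A shift common to both conditions cancels, and seeing an up or down code does not reveal which one is anodal. The protection does depend on the scorer being blind to condition, and the Blinding section names staff who interact with patients rather than an offline scorer.

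**Scoring discretion is limited.** This stands in part. Targets are single pictured nouns, responses are recorded and transcribed so they can be audited, and the response to be scored is fixed in advance. What counts as complete and accurate is still left to the scorer.

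**The rates are hypothetical.** This stands. No document gives a leniency figure, an SD or an alpha. Converting the shift into items out of 75 would also mislead, because 75 is the total of trained and untrained nouns in a list and the endpoint treats the two sets separately. Zero true change is hard to credit for trained items after a week of practice, so 63% should not be read as the chance that this trial reaches a false conclusion.

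**Masking would not rescue Aim 1.** This stands, but it concerns something else. Aim 1 has no comparator, so therapy and practice effects remain mixed with any tDCS effect however the recordings are scored. Scorer bias is an additional error, and a removable one.

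**Conclusion.** The concern holds for Aim 1. The declared double blind does not extend to visit, the plan has no provision that does, and an uncontrolled pre-post test cannot be protected by blinding to condition.

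The size is unknown. Under the assumptions above, the effect is negligible at a shift of 0.1 SD (7% at n=24, 5% at n=12), noticeable at 0.25 SD (21% and 12%) and serious at 0.5 SD (63% and 32%). These figures show how sensitive the test is to a scoring shift; they do not predict that one will occur.

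The documents do not support the stronger readings: that the scorer is known to be unmasked, that Aim 2 is biased, or that masking would make Aim 1 evidence of a tDCS effect. The point is a cheap improvement to how the primary measure is scored, and best made before scoring begins.

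**What to change.** Add to the Naming Probes and Blinding sections that:

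1. each naming recording receives a random ID, with visit, date, period and switch code removed;
2. all of a participant's recordings are pooled and scored in random order by the existing SLP scorer, after that participant's last visit.

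Recording for later scoring is already planned, so no extra visits, participants or assessors are needed, and treatment is unchanged. The cost is the relabelling work and scores that arrive later. If this is already the practice, stating it in the plan is enough.

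The change removes scorer bias by visit. Removing the switch code also secures the condition blinding on which Aim 2's protection depends. It does not give Aim 1 a comparator, and any Aim 1 result should still be described as change after stimulation plus therapy.

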Methods to address specific aim 3: This will be examined with a 2x2 repeated measures ANOVA with change in naming performance in each stimulation condition (change in naming performance A-tDCS vs. S-tDCS) and severity level (high vs. low functioning aphasia).

Protection of Human Subjects

RISKS TO SUBJECTS

Human Subject Involvement and Characteristics: We anticipate enrolling 12 human subjects. Inclusion and exclusion criteria are stated above in the Research Design and Methods section.

Sources of Material: Sources of research material will be the hospital records providing demographic and medical information including CT or MRI imaging studies, and clinical examinations performed at outpatient facilities run by the Department of Physical Medicine and Rehabilitation of the North Shore University Hospital (NSUH) and LIJ Medical Center (LIJMC), or copies of medical records from outside hospitals provided by participants.

Potential Risks:

tDCS Risks: tDCS is a safe technique that poses a non-significant risk to participants. The safety of this technique has been addressed and tested by multiple researchers (16, 18, 20, 33-34) who have concluded that tDCS, as applied in a manner similar to our proposed protocol has no long-term negative side effects. More than 30 research studies involving hundreds of participants have been published using tDCS. Hundreds more participants have undergone tDCS for unpublished pilot research. No undesirable or long-lasting effects have been reported, nor have any participants reportedly abandoned a study due to discomfort.

Researchers at the National Institute of Neurological Disorders and Stroke (NINDS) conducted a safety study on tDCS, investigating 20-minute sessions of 1 mA and 2 mA current stimulation with healthy controls (n=103) (20). No negative effects were identified. Nitsche and colleagues (2004) found no measurable structural changes in brain tissue due to tDCS (23). Additionally, studies have shown that tDCS can be used safely in stroke patients (11, 18, 34-37). Thus, a growing body of research from different laboratories has shown that tDCS is a safe, non-invasive and painless technique for modulating neural excitability, with measurable but only transient effects. The protocol described here uses stimulation levels that fall well within safety limits established by basic research investigating neural tissue damage, as well as

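### Stimulation order has no stated balance within severity groups and the Aim 3 model has no period term, so a practice effect can shift the severity-by-stimulation interaction by chance

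*Combined protocol and SAP*

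**What the plan says.** All references are to the combined protocol and SAP.

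- **Allocation.** The Randomization section says "The order of anodal or sham stimulation will be counterbalanced across participants, and determined using a random number generator". The Visit Schedule extends this to the word lists: "Order of training word lists and tDCS stimulation condition will be counterbalance across participants". Neither place names severity, a stratum or a block.
- **Aim 3 analysis.** Under Statistical Considerations and Data Analysis, Specific Aim 3 plans a two-by-two ANOVA for repeated measures. Its factors are given as "change in naming performance in each stimulation condition (change in naming performance A-tDCS vs. S-tDCS) and severity level (high vs. low functioning aphasia"). Period, order and sequence do not appear.
- **Severity groups.** They are "high vs. low functioning aphasia as determined by admission Western Aphasia Battery scores (WAB"). No cut-off and no planned group sizes are given.
- **When severity is known.** The inclusion criteria require "A baseline Aphasia Quotient score between 10 to 94 out of 100 points on the Western Aphasia Battery". The Schedule Chart places inclusion criteria and outcome measures at Visit 1, and stimulation starts at Visit 3.
- **Sample size.** The Visit Schedule says "In this pilot study, 24 participants will be accepted from our referral sources", while Protection of Human Subjects says "We anticipate enrolling 12 human subjects". Both figures are used below.

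**The concern.** In a two-period crossover, each participant's anodal-minus-sham difference also contains the difference between first and second period, with a sign set by the order received. Balancing order over the whole sample cancels this for the average effect, which is Aim 2. It cancels for the severity-by-stimulation interaction only if both severity groups have the same share of anodal-first participants, and nothing stated ensures that.

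A non-zero period effect is plausible here. The same computerized task is repeated after a one-week rest, and the Preliminary Data section describes a cited aphasia study whose gains persisted at 1 and 3 weeks. The pre-training score for the second condition is also not defined. If it is taken from the lead-in visits, any general gain from the first training week is credited to the second condition.

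At stake is the reading of the interaction. If more high-functioning participants happened to receive anodal first, an ordinary practice gain would look like a weaker response to tDCS in that group. The reverse imbalance would look like a stronger one.

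**Working it through.** The plan states no power, SD or balance figure, so there is nothing to reproduce.

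**1. Size of the shift.** Let D = change under anodal minus change under sham, τ = the stimulation effect, P = period 2 gain minus period 1 gain from practice alone, and p = the share anodal-first. Then D averages τ − P if anodal is first and τ + P if sham is first. The mean of D in severity group g is τ_g + P(1 − 2p_g), and the interaction contrast is

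(τ_high − τ_low) − 2P(p_high − p_low).

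Averaged over the whole sample with p = 1/2, the P term is zero, so Aim 2 is protected. The severity main effect averages both periods in every participant, so order drops out.

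**2. How uneven order can be.** Assume equal severity groups and a 50:50 order split overall. The number anodal-first in the high group, X, is then hypergeometric.

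| | N = 24 (12 per group) | N = 12 (6 per group) |
|---|---|---|
| Exact balance | C(12,6)²/C(24,12) = 0.316 | C(6,3)²/C(12,6) = 400/924 = 0.433 |
| Share difference ≥ 1/3 | 0.22 | 0.57 |
| Larger imbalance | ≥ 1/2: 0.04 | ≥ 2/3: 0.08 |
| SD of X | √(36/23) = 1.251 | √(9/11) = 0.905 |
| SD of p_high − p_low | 1.251/6 = 0.209 | 0.905/3 = 0.302 |
| SD of shift | 0.42P | 0.60P |

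A share difference of 1/3 (8/12 against 4/12, or 4/6 against 2/6) gives a shift of 2P × 1/3 = 0.67P. With a 1:2 severity split the SD of the shift is 0.44P (N = 24) or 0.64P (N = 12).

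**3. Effect on the test.** Assumptions not in the documents: SD of D given order = 1, two-sided alpha 0.05, P = 0.5 or 1 SD of D, equal severity groups, true interaction 1.2 SD for power. Rates are simulated, with 6,000 runs per setting.

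- *Precision, P = 1.* At N = 24 the SD of the contrast is √(1/12 + 1/12 + 0.417²) = 0.58, against √(1/12 + 1/12) = 0.41 with order balanced within groups. At N = 12 the figures are 0.83 and 0.58.
- *Type I error over all allocations, model as written.* About 0.05 at both sample sizes.
- *Type I error given the imbalance, model as written, N = 24.* About 0.10 (P = 0.5) to 0.13 (P = 1) at a share difference of 1/3. At 1/2 it is about 0.18 to 0.38, from only some 200 runs each.
- *The same at N = 12.* About 0.05 at 1/3, and 0.15 to 0.31 at 2/3.

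| Power, N = 24 | P = 0.5 | P = 1 |
|---|---|---|
| As planned | about 70% | about 50% |
| Order balanced within severity, no period term | about 72% | about 50% |
| Period term, no stratification | about 80% | about 78% |
| Both | about 80% | about 80% |

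Stratifying without a period term leaves P in the error variance. The test becomes conservative (type I error about 0.03 at P = 0.5, below 0.01 at P = 1) and power hardly moves.

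At N = 12, power as planned is about 38% (P = 0.5) or 24% (P = 1). A period term alone gives 42 to 43%, and both changes give 45 to 47%. If P = 0, the period term alone costs about 1 point of power at N = 24 (81% to 80%) and 5 points at N = 12 (48% to 42%).

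**The case against.** The strongest reply is that this is ordinary chance imbalance in a randomised pilot. The expected shift is zero and the test keeps its nominal error rate over repeated allocations. At N = 24, exact balance (32%) and 7:5 against 5:7 (46%) together cover 78% of allocations, with a shift of at most 0.33P. At N = 12 the 57% is simply the chance of any imbalance, since 4:2 against 2:4 is the smallest possible. P is not given, and using a different word list in each condition should reduce practice effects. All of this stands, and it limits the importance of the point.

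A reader might infer that the Aim 3 interaction could not be separated from a practice effect. That does not follow. Order is known for every participant and both periods are observed, so a period term removes a common shift without any stratification. Only complete confounding of order with severity would prevent it.

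A reader might also infer that stratified allocation alone would cure the problem. It would not, as the power table shows. Nor do the documents rule out stratification; they are silent on it.

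Two practical objections also stand. Severity groups formed at the sample median could not be used as strata, because the median is unknown at allocation. Word lists raise the same issue: unequal list difficulty can leak by the same route, and order, list and severity together make 2 × 2 × 2 = 8 cells for 24 or 12 participants.

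The objection does not remove the gap. The trial is allocated once, and exact balance is the less likely result at either sample size. As written, neither the allocation nor the model guards the interaction.

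**Conclusion.** The point holds as a modest, cheaply corrected weakness in one contrast: the severity-by-stimulation interaction of Aim 3. In the realised allocation a period effect P shifts that contrast by 2P times the difference in anodal-first share, with SD 0.42P (N = 24) or 0.60P (N = 12) under equal severity groups. If P is zero, nothing leaks.

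It should not be read as systematic bias, as an inflated overall error rate, or as a flaw in Aim 2 or in the severity main effect. The main defect is the missing model term; the unstratified allocation is secondary. The power and conditional error figures rest on assumed values of P and of the interaction. The sample-size conflict should be reconciled, because the shift is more variable at 12.

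**What to change.** 1. **Model.** Add period as a within-participant factor to the Aim 3 analysis. Equivalently, regress each participant's anodal-minus-sham difference on severity and stimulation order. A between-participant order main effect alone in the repeated measures ANOVA would not suffice; it must be allowed to interact with stimulation. This removes a period effect common to both severity groups and takes it out of the error term.
2. **Allocation.** State a Western Aphasia Battery Aphasia Quotient cut-off before the first allocation. Generate stimulation order in short permuted blocks within the two severity groups, keeping the word-list counterbalancing. Blocks of four holding each order-by-list combination once would do both; 12 per group makes three complete blocks, and 6 per group leaves one incomplete. By the algebra above, p = 1/2 within each group also removes the shift if P differs between severity groups, which a single period term does not.

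**Cost.** A few sentences, two randomisation lists instead of one, and no added visits or data. The cut-off must be prospective, which excludes a sample-median split. One error degree of freedom is used, which matters more at 12 participants than at 24. The model change can still be made before unblinding; the allocation change has to precede the first assignment.
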